6.6 Dose escalation and dose modification

Investigational or other study treatment dose adjustments are not permitted.

Study treatment interruptions are permitted in order to manage the following events:

- Management of bleeding events: in case of planned surgery with clinical significant bleeding risk, interruption of study treatment 7 days before the surgery is required; after recovery, participant may re-start study treatment after 7 days.
- Management of participants in case of Hepatitis B re-activation (new appearance of detectable HBV-DNA or positive HBsAg): participants should start antiviral treatment according to local clinical practice and interrupt study treatment until HBV-DNA and HBsAg reach an undetectable level, and then re-start study treatment.

Study treatment interruption for other than the above reasons is only permitted if, in the opinion of the investigator, a participant is deemed to be at a significant safety risk unless administration of investigational treatment is temporarily interrupted. In such cases study treatment should be interrupted only during the time that this risk is present and ongoing. Study treatment can be re-started at the next scheduled visit after resolution of the safety risk.

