9.1.1 Discontinuation from study treatment

Discontinuation of study treatment for a participant occurs when study treatment is permanently stopped for any reason (prior to the protocol planned completion of study drug administration) and can be initiated by either the participant or the investigator.

The investigator must discontinue study treatment for a given participant if, he/she believes that continuation would negatively impact the participant's well-being.

Discontinuation from study treatment is required under the following circumstances:

- Participant decision (requested in writing or verbally)

- Pregnancy
- Use of prohibited treatment requiring study treatment discontinuation as detailed in [Table 6-3](#) or discontinuation of highly effective methods of contraception as detailed in [Section 5.2](#)
- Any situation in which continued study participation might result in a safety risk to the participant
- Following emergency unblinding
- Emergence of the following AEs:
 - any adverse events that in the judgement of investigator, taking into consideration the participant's overall status, prevents the participant from continuing participation in the study, including:
 - hypersensitivity reactions,
 - severe/serious infections,
 - clinically significant spontaneous bleeding events
 - new confirmed diagnosis of malignancy of any organ system
(other than localized basal cell carcinoma of the skin or in situ cervical cancer)
 - Platelets < 75 000/mm³
 - Abnormal renal laboratory results requiring discontinuation (see [Section 16.3](#))
 - Abnormal liver laboratory results requiring discontinuation (see [Section 16.2](#))
 - Any other laboratory abnormalities that in the judgment of the investigator, taking into consideration the participant's overall status, prevents the participant from continuing participation in the study
 - participant received a live virus vaccination during the study

[figure not shown]
If discontinuation from study treatment occurs, the investigator should make a reasonable effort to understand the primary reason for the participant's discontinuation from study treatment and record this information.

All participants who discontinue from study treatment prematurely should complete the Early treatment discontinuation visit at the time of treatment discontinuation.

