10.2 Additional Safety Monitoring

10.2.1 Liver safety monitoring

To ensure participant safety and enhance reliability in determining the hepatotoxic potential of an investigational drug, a standardized process for identification, monitoring and evaluation of liver events has to be followed.

Please refer to [Table 16-1](#) in [Section 16.2](#) for complete definitions of liver laboratory triggers.

Once a participant is exposed to study treatment, every liver event defined in [Table 16-1](#) should be followed up by the investigator or designated personnel at the trial site, as summarized below. Additional details on actions required in case of liver events are outlined in [Table 16-2](#) and [Table 16-3](#). Repeat liver chemistry tests (i.e., ALT, AST, TBL, PT/INR, ALP and GGT) to confirm elevation.

These liver chemistry repeats will be performed using the central laboratory. If results will not be available from the central laboratory, then the repeats can also be performed at a local laboratory to monitor the safety of the participant. If a liver event is subsequently reported, any local liver chemistry tests previously conducted that are associated with this event should have results recorded on the appropriate CRF.

- If the initial elevation is confirmed, close observation of the participant will be initiated, including consideration of treatment interruption if deemed appropriate.
- Discontinuation of the investigational drug (refer to [Section 9.1](#) and [Section 16.2](#)), if appropriate
- Hospitalization of the participant if appropriate
- Causality assessment of the liver event
- Thorough follow-up of the liver event should include, based on investigator's discretion:
 - serology tests, imaging and pathology assessments, hepatologist's consultancy; obtaining more detailed history of symptoms and prior or concurrent diseases, history of concomitant drug use, exclusion of underlying liver disease

All follow-up information and procedures performed must be recorded as appropriate in the CRF.

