16.2 Appendix 2: Liver event and laboratory trigger definitions & follow-up requirements

Table 16-1 Liver event and laboratory trigger definitions

	Definition/ threshold
Liver laboratory triggers If ALT, AST and total bilirubin normal at baseline:	
 • ALT or AST > 5 × ULN • ALP > 2 × ULN (in the absence of known bone pathology) • Total bilirubin > 3 × ULN (in the absence of known Gilbert syndrome) • ALT or AST > 3 × ULN and INR > 1.5 • Potential Hy's Law cases (defined as ALT or AST > 3 × ULN and Total bilirubin > 2 × ULN [mainly conjugated fraction] without notable increase in ALP to > 2 × ULN) • Any clinical event of jaundice (or equivalent term) • ALT or AST > 3 × ULN accompanied by (general) malaise, fatigue, abdominal pain, nausea, or vomiting, or rash with eosinophilia • Any adverse event potentially indicative of a liver toxicity

ALP: Alkaline phosphatase, ALT: Alanine aminotransferase, AST: Aspartate aminotransferase, ULN: upper limit of normal

Table 16-2 Follow up requirements for liver laboratory triggers ALT, AST, and TBL

Trigger	Liver Symptoms	Action Taken		
		Monitoring	Follow-up Monitoring	Study Medication
ALT				
ALT > 3 ULN TBL normal, or no change for participants with Gilbert's syndrome	None	Measure ALT, AST, ALP, GGT, TBL, INR, albumin, CK, and GLDH in 48-72 hours	Follow up for symptoms	Continue dosing
ALT > 5 x ULN for more than two weeks TBL normal, or no change for participants with Gilbert's syndrome	None	Measure ALT, AST, ALP, GGT, TBL, INR, albumin, CK, and GLDH in 48-72 hours	Follow-up for symptoms Initiate close monitoring and workup for competing etiologies	Interrupt Study drug can be restarted only if another etiology is identified and liver enzymes return to baseline

Trigger	Liver Symptoms	Action Taken		
		Monitoring	Follow-up Monitoring	Study Medication
ALT > 8 x ULN TBL normal, or no change for participants with Gilbert's syndrome	None	Measure ALT, AST, ALP, GGT, TBL, INR, albumin, CK, and GLDH in 48-72 hours	Follow-up for symptoms Initiate close monitoring and workup for competing etiologies	Interrupt Study drug can be restarted only if another etiology is identified and liver enzymes return to baseline

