ALT > 3 x ULN TBL > 2 x ULN (or INR > 1.5) For participants with Gilbert's syndrome: Doubling of direct bilirubin	None	Measure ALT, AST, ALP, GGT, TBL, INR, albumin, CK, and GLDH in 48-72 hours	Follow-up for symptoms Initiate close monitoring and workup for competing etiologies	Interrupt Study drug can be restarted only if another etiology is identified and liver enzymes return to baseline
ALT > 3 x ULN TBL normal or elevated	Severe fatigue, nausea, vomiting, right upper quadrant pain	Measure ALT, AST, ALP, GGT, TBL, INR, albumin, CK, and GLDH in 48-72 hours	Follow-up for symptoms Initiate close monitoring and workup for competing etiologies	Interrupt Study drug can be restarted only if another etiology is identified and liver enzymes return to baseline
Total Bilirubin (isolated)				
>1.5 – 3.0 ULN		Repeat LFTs within 48-72 hours	Monitor LFTs weekly until resolution ¹ to ≤ Grade 1 or to baseline	Continue dosing
> 3 - 10 × ULN (in the absence of known Gilbert syndrome)		Repeat LFT within 48-72 hours Hospitalize if clinically appropriate Establish causality Record the AE and contributing factors (e.g., conmeds, med hx, lab) in the appropriate CRF	Monitor LFTs weekly until resolution ¹ to ≤ Grade 1 or to baseline (ALT, AST, total bilirubin, Alb, PT/INR, ALP and GGT) Test for hemolysis (e.g., reticulocytes, haptoglobin, unconjugated [indirect] bilirubin)	Interrupt
> 10 x ULN		Hospitalize the participant Establish causality	ALT, AST, total bilirubin, Alb, PT/INR, ALP and GGT until	Discontinue treatment immediately

		Action Taken		
Trigger	Liver Symptoms	Monitoring	Follow-up Monitoring	Study Medication
		Record the AE and contributing factors (e.g., conmeds, med hx, lab) in the appropriate CRF	resolution ¹ (frequency at investigator discretion)	
General Clinical Symptoms				
Any AE potentially indicative of a liver toxicity including: (General) malaise, fatigue, abdominal pain, nausea, or vomiting, or rash with eosinophilia		Establish causality Record the AE and contributing factors (e.g., conmeds, med hx, lab) in the appropriate CRF	Investigator discretion	Consider study treatment interruption or discontinuation

¹ Resolution is defined as an outcome of one of the following: (1) return to baseline values, (2) stable values at three subsequent monitoring visits at least 2 weeks apart, (3) remain at elevated level after a maximum of 6 months, (4) liver transplantation, and (5) death

[figure not shown]

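### The Table 16-2 row for potential Hy's Law or raised INR is keyed on ALT alone, so an AST-defined case has no AST-specific mandatory interruption and no liver-specific restart limit.

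*Protocol*

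**What the plan says.** Protocol Table 16-1 (Section 16.2, Appendix 2) lists eight liver triggers. Four can be met by either aminotransferase: above 5 × ULN; above 3 × ULN with INR above 1.5; potential Hy's Law; and above 3 × ULN with symptoms. The Hy's Law entry begins "Potential Hy's Law cases (defined as ALT or AST" and goes on to require more than 3 × ULN, total bilirubin above 2 × ULN and no notable rise in ALP.

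Section 10.2.1 asks for follow-up of every event in Table 16-1. It adds: "Additional details on actions required in case of liver events are outlined in" Tables 16-2 and 16-3. Table 16-2 is titled "Follow up requirements for liver laboratory triggers ALT, AST, and TBL". For ALT above 3 × ULN with total bilirubin above 2 × ULN or INR above 1.5, it orders interruption and states: "Study drug can be restarted only if another etiology is identified and liver enzymes return to baseline". For adverse events that may indicate liver toxicity, it says "Consider study treatment interruption or discontinuation".

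Three other provisions bear on the point:
- Section 10.2.1 calls for close observation of a confirmed elevation, "including consideration of treatment interruption if deemed appropriate".
- Section 9.1.1 lists among the reasons that require discontinuation "Any situation in which continued study participation might result in a safety risk to the participant".
- Section 6.6 sets the general restart rule: "Study treatment can be re-started at the next scheduled visit after resolution of the safety risk".

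**The concern.** The definitions treat the two enzymes alike, but the actions do not. Two participants can meet the same protocol definition of potential Hy's Law. The one who meets it through ALT must be interrupted and cannot restart unless another cause is found. For the one who meets it through AST alone, the liver section contains no corresponding order, and what happens depends on general clauses and the investigator's reading of them.

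This is a participant-safety matter. Rechallenge after an unexplained Hy's Law pattern is what the ALT row is written to prevent, and Section 10.2.1 presents liver follow-up as a standardized process. The stake is whether that protection covers everyone who meets the definition.

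**Working it through.** No arithmetic beyond counting applies, so the check sets the tables side by side.

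**Step 1. Count the rows of Table 16-2.** There are 5 ALT rows (1 continue, 4 interrupt), 0 AST rows, 3 rows for isolated bilirubin and 1 for general symptoms: 5 + 0 + 3 + 1 = 9. In the body of the table AST appears only as a test to measure. The blocks run on without a redaction mark or gap where AST rows might have been.

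**Step 2. Map each shared trigger to its action.**

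| Table 16-1 trigger | Met by ALT | Met by AST, with ALT at or below 3 × ULN |
|---|---|---|
| > 3 × ULN with bilirubin > 2 × ULN (potential Hy's Law) | Interrupt at once, restart limited | No enzyme row; liver adverse-event rows say consider |
| > 3 × ULN with INR > 1.5 | Interrupt at once, restart limited | No enzyme row; liver adverse-event rows say consider |
| > 5 × ULN | Interrupt with restart limit only if it lasts more than two weeks or exceeds 8 × ULN; otherwise continue dosing (bilirubin normal) | No enzyme row; liver adverse-event rows say consider |
| > 3 × ULN with symptoms | Interrupt with restart limit for nausea, vomiting, severe fatigue or right-upper-quadrant pain; otherwise consider | Consider |

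For ALT, 2 of the 4 triggers lead directly to mandatory interruption and the other 2 do so conditionally. For AST alone, 0 of 4 do.

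**Step 3. Try the bilirubin rows for an AST-defined Hy's Law case.** They are labelled as isolated bilirubin, so they do not fit a case with raised AST. If a site used them anyway:
- bilirubin above 2 and up to 3 × ULN falls in the band that continues dosing;
- above 3 and up to 10 × ULN is interrupted, with no condition about another cause;
- above 10 × ULN is discontinued immediately.

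The middle band does give an interruption, but the lowest does not.

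**Step 4. Look for a rule elsewhere.**
- Table 16-3 has a row for any adverse event that may indicate liver toxicity. Under Section 10.1.1 a clinically significant laboratory value is an adverse event, so an AST trigger can reach that row. The instruction is again to consider interruption or discontinuation.
- Section 10.2.1 covers AST-defined events for repeat testing, close observation and causality assessment, but leaves interruption to what is deemed appropriate.
- Section 9.1.1 sends abnormal liver results back to Section 16.2. Its safety-risk clause is a requirement, but it names no laboratory pattern.
- Section 6.6 requires the risk to have resolved and a scheduled visit to be reached before restart. It sets no condition about cause or return of enzymes to baseline.

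**Step 5. Compare with the SAP.** Table 2-16 (SAP Section 2.7.3) uses ALT or AST for both the INR combination and potential Hy's Law. That agrees with Protocol Table 16-1 and not with the action row.

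**The case against.** The strongest reply is that AST-defined cases are not left unprotected. Section 9.1.1 requires discontinuation where continuing might pose a safety risk. Unlike neighbouring items in its list, that clause carries no reference to investigator judgement. The investigator must also stop treatment if continuation is believed to harm the participant. A competent investigator facing an AST-defined Hy's Law pattern would very likely act on these clauses. All of this stands. It does not supply a rule tied to the AST pattern, and it puts no liver-specific condition on restart.

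A reader might infer a clean contrast in which all four ALT triggers force interruption and no AST trigger does. The documents do not support that. ALT of 6 × ULN for under two weeks with normal bilirubin means continued dosing, and the ALT symptom row is narrower than the symptom trigger. Table 16-2 was also never a full map of Table 16-1: the ALP trigger has no row of its own. The firm contrast is confined to the bilirubin and INR combinations.

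Keying on ALT could also be deliberate, because AST can come from muscle, and CK in the work-up is compatible with that. No such reason is stated, however, and the title says the opposite. Exclusion criterion 21 and SAP Table 2-16 treat the two enzymes alike.

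Finally, the pattern needs AST above 3 × ULN with ALT at or below it, in a population screened for liver disease and for AST or ALT above 1.5 × ULN. It is probably uncommon. That limits the number affected but does not remove the inconsistency.

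**Conclusion.** The concern holds for the two combined triggers, potential Hy's Law and raised INR. When AST alone crosses 3 × ULN, the protocol gives no AST-specific mandatory interruption and no liver-specific restart limit. For the other two shared triggers the gap is less clear-cut, because the ALT rule is itself conditional.

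The number of participants affected cannot be stated from the documents. The conclusion rests on the table being complete as reproduced and on ALT staying at or below 3 × ULN; if ALT also crosses, the ALT row applies.

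Three stronger readings should be resisted:
- That restart is unrestricted: Section 6.6 still sets a general condition.
- That the SAP will reveal the size of the gap by subtracting its ALT line from its ALT-or-AST line. Table 2-16 has no ALT-only Hy's Law line, and at cut-offs of 5 × ULN and above the difference can include participants whose ALT exceeded 3 × ULN.
- That the hepatotoxicity assessment would be biased by mixing cases handled under different rules. The planned graphs are per participant and show treatment exposure, so each case's dosing can be seen.

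The point is one of participant safety and internal consistency. Efficacy analyses are not affected. It should be corrected because the remedy is nearly free and follows the protocol's own definition.

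**What to change.** In the Table 16-2 row for ALT above 3 × ULN with total bilirubin above 2 × ULN or INR above 1.5, replace ALT with ALT or AST. For the other three ALT rows that order interruption, either make the same change or state that AST is left out on purpose, give the reason, and correct the table title.

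The cost is one cell, or up to four, in a protocol amendment. The change adds no assay beyond the work-up that the row already prescribes. The downside is an occasional interruption for an AST rise of muscle origin. CK is in that work-up and can help identify such a case, so treatment can restart under the row's existing conditions once enzymes are back at baseline. New restart rules for isolated bilirubin, a permanent-discontinuation rule in Section 6.6 or a rewrite of Section 10.2.1 do not follow from the missing AST label and are not proposed here.

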 - Drug interrupted/permanently discontinued
6. Its outcome (i.e., recovery status or whether it was fatal)

Conditions that were already present at the time of informed consent should be recorded in medical history of the participant.

Adverse events (including lab abnormalities that constitute AEs) should be described using a diagnosis whenever possible, rather than individual underlying signs and symptoms.

Adverse event monitoring should be continued for at least 30 days following the last dose of study treatment.

Once an adverse event is detected, it must be followed until its resolution or until it is judged to be permanent (e.g., continuing at the end of the study), and assessment must be made at each visit (or more frequently, if necessary) of any changes in severity, the suspected relationship to the interventions required to treat it, and the outcome.

Information about adverse drug reactions for the investigational drug can be found in the Investigator's Brochure (IB).

Abnormal laboratory values or test results constitute adverse events only if they fulfill at least one of the following criteria:

- they induce clinical signs or symptoms
- they are considered clinically significant
- they require therapy

Clinically significant abnormal laboratory values or test results must be identified through a review of values outside of normal ranges/clinically notable ranges, significant changes from baseline or the previous visit, or values which are considered to be non-typical in participant with the underlying disease. See [Section 16.1](#) , [Section 16.2](#) and [Section 16.3](#) for alert ranges for laboratory and other test abnormalities.

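### Table 16-2's numeric mandatory interruption at high ALT, and its restart condition, lapse when total bilirubin is mildly raised (> 1 to 2 x ULN) and return above 2 x ULN

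*Protocol*

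**What the plan says.** Protocol Section 16.2, Table 16-2 sets the study-medication action for raised ALT. Two rows for participants without symptoms require interruption on ALT with normal bilirubin: "ALT > 5 x ULN for more than two weeks TBL normal, or no change for participants with Gilbert's syndrome" and "ALT > 8 x ULN TBL normal, or no change for participants with Gilbert's syndrome". Both carry the same restart rule: "Study drug can be restarted only if another etiology is identified and liver enzymes return to baseline".

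The next asymptomatic row, also *Interrupt* with that restart rule, is "ALT > 3 x ULN TBL > 2 x ULN (or INR > 1.5) For participants with Gilbert's syndrome: Doubling of direct bilirubin". One further ALT row accepts any bilirubin level, but only with listed symptoms. The bilirubin rows in Tables 16-2 and 16-3 are for isolated elevations.

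A general row for "Any AE potentially indicative of a liver toxicity including" various symptoms gives the action "Consider study treatment interruption or discontinuation". Under Section 10.1.1 an abnormal laboratory value is an adverse event only if it causes signs or symptoms, needs therapy, or meets the criterion "they are considered clinically significant".

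Table 16-1 makes ALT or AST above 5 x ULN a liver trigger, under the heading "If ALT, AST and total bilirubin normal at baseline". For such an event Section 10.2.1 asks for repeat chemistry, close observation, a causality assessment, and thought about interrupting treatment.

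**The concern.** A stopping rule for liver injury should not become weaker as a second liver marker worsens. Here it does over one range. At the same high ALT, the participant with bilirubin between 1 and 2 x ULN loses the numeric stop that protects the participant with normal bilirubin. The restart condition goes with it, so treatment could resume without another cause having been found. No rationale is given. The symptomatic row, which accepts normal or elevated bilirubin, shows that the authors could write a row for any bilirubin level when they meant one.

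The sponsor itself treats part of this combination as informative. SAP Table 2-16 counts ALT or AST > 3 x ULN with TBL > 1.5 x ULN separately from TBL > 2 x ULN when assessing potential drug-induced liver injury.

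**Working it through.** No sample size, power or error rate is involved. The check reads the ALT rows of Table 16-2 as conditions and asks which row matches.

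**Assumptions.** No symptoms, no Gilbert's syndrome, INR 1.0. Table 16-2 gives no number for normal bilirubin, so it is taken as TBL <= 1 x ULN. Where a participant with normal bilirubin matches both the ALT > 3 x ULN row (*Continue dosing*, no upper ALT limit) and a higher row, the higher row is taken to govern. The table does not say so.

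| ALT (x ULN) | TBL 0.9, 1.0 | TBL 1.1, 1.5, 1.8, 2.0 | TBL 2.1 |
|---|---|---|---|
| 4 | Continue | no ALT row | Interrupt |
| 6, more than two weeks | Interrupt + restart rule | no ALT row | Interrupt + restart rule |
| 9 | Interrupt + restart rule | no ALT row | Interrupt + restart rule |
| 15, more than two weeks | Interrupt + restart rule | no ALT row | Interrupt + restart rule |

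At ALT 9 and TBL 1.5 x ULN, adding listed symptoms or raising INR to 1.6 brings back mandatory interruption. The qualifiers on symptoms and INR are therefore needed. At ALT 4 x ULN nothing is reversed, because the action at normal bilirubin is already to continue.

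**What else applies at ALT above 8 x ULN (or above 5 x ULN for more than two weeks) with TBL > 1 to 2 x ULN.**

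| Provision | What it requires | Condition |
|---|---|---|
| Table 16-2, general adverse-event row | Establish causality; consider interrupting or discontinuing | Value judged to be an adverse event |
| Section 10.2.1 | Repeat tests, causality assessment, close observation once confirmed; consider interruption | Table 16-1 event, which presupposes normal baseline values |
| Section 6.6 | Permits interruption; restart at the next scheduled visit once the risk has gone | Investigator sees a significant safety risk |
| Section 9.1.1, required list | Discontinuation where continuing might endanger the participant | Someone recognises the risk; no number given |
| Section 9.1.1, liver criterion | Refers back to Section 16.2 | Adds no threshold of its own |

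The Section 10.2.1 condition may not always hold. Exclusion criterion 21 admits ALT and AST up to 1.5 x ULN and sets no numeric bilirubin limit, so an eligible participant may not have had normal values at baseline.

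None of these provisions restates the etiology-based restart condition.

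**The case against.** **A mandatory rule still exists.** A reader might infer that nothing in the protocol compels a stop inside the band. The documents do not support that. Section 9.1.1 lists any situation that might put the participant at risk among those requiring discontinuation. That threshold is low, the consequence is stronger than interruption, and ALT above 8 x ULN with raised bilirubin plausibly meets it. This part of the objection stands. What remains is that the rule has no numeric trigger and works only if someone recognises the risk, whereas the Table 16-2 rows work from the laboratory value.

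**The table is meant as a ladder.** ALT 9 x ULN with normal bilirubin also matches the *Continue dosing* row, so the table makes sense only if the stricter row governs. A site reading it that way would hardly treat extra bilirubin as cancelling the ALT > 8 action. That is a fair account of likely practice. But the text states no such precedence, and a ladder reading does not remove the explicit bilirubin condition in the two rows.

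**Monitoring continues and exposure is small.** A reader might infer that these participants go unwatched. They do not: when the Table 16-1 event applies, repeat chemistry, close observation and causality assessment follow, and a DMC reviews safety data. Screening excludes hepatic disease. The band also closes if bilirubin normalises or passes 2 x ULN, INR passes 1.5, or listed symptoms appear. This limits the size of the problem but does not supply the missing stop or restart rule.

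**Part of the band is mild.** Isolated bilirubin up to 1.5 x ULN triggers no action in Tables 16-2 and 16-3, and Table 16-3 counts that level as resolution. So the concern is smaller at TBL > 1 to 1.5 x ULN.

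**Conclusion.** The gap is real and narrow. For asymptomatic participants without Gilbert's syndrome and with INR <= 1.5, at ALT > 8 x ULN or > 5 x ULN for more than two weeks, the numeric interruption and the restart condition apply at normal bilirubin, lapse at TBL > 1 to 2 x ULN, and return above 2 x ULN. In between, a stop rests on judgment, including the judgment needed to invoke the required discontinuation in Section 9.1.1. The clearest loss is the restart condition.

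The sequence of actions at normal bilirubin assumes that the stricter row governs there. The documents give no frequency, and the case is expected to be rare. It matters most at TBL > 1.5 to 2 x ULN. It should be corrected on safety grounds.

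**What to change.** In Table 16-2, delete the bilirubin clause, with its Gilbert's alternative, from the row for ALT > 5 x ULN lasting more than two weeks and from the row for ALT > 8 x ULN. Both then apply at any bilirubin level, with the restart condition attached.

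Add one line under the table saying that when more than one row could apply, the most restrictive study-medication action prevails. This also settles the overlap with the ALT > 3 x ULN *Continue dosing* row.

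With both changes, every asymptomatic participant at those two ALT levels is at least interrupted. Lower ALT with TBL > 1 to 2 x ULN would still match no ALT row, but no mandatory stop is lost there because the row at normal bilirubin is *Continue dosing*.

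The cost is a wording change to one appendix table, by amendment or clarification letter, with no new tests. The downside is a few more mandatory interruptions and fewer restarts. SAP Section 2.5.1.3 already handles dose interruption before Week 12 by treatment policy, so the primary analysis method does not change.
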